When estimating the model in (i), for our primary analysis we plan to only use observations from the post-period. This avoids any contamination from outcomes of ED observations when DA was not available. However, to gain some insight into the closeness of the results from this analysis with those that we'd expect to see if it was possible to have patient-level randomization, in a supplemental analysis we will include the pre-intervention ED observations and test if there is a change in the mean ED outcome in the post-intervention period. A result consistent with minimal change over time will support a finding that, in the absence of the intervention, the outcomes for DA patients would have been the same as those observed for ED patients.

The statistical model for analysis (ii) has a similar form:

$$Y_{ijht} = \beta_0 + \beta_1 Post_{jht} + \beta_2 x_{ijht} + \beta_{3t} + \beta_{4h} + \theta_{jh} + \varepsilon_{ijht}$$

differing only in that the direct admission indicator is replaced with $Post_{jht}$, a time-varying practice within hospital indicator of whether the intervention has been rolled-out (1 = intervention transition has occurred by time period t and 0 = direct admission intervention has not occurred by time-period t). The key coefficient of interest is β_1 , which captures the structural shift in the outcome that occurs when a practice receives the direct admission intervention. Because $Post_{jht}$ does not vary within a clinic and time-period, the information in the observations made within a clinic and time-period depends on the size of the effects of clinic and time-period with the statistical significance of inferences about β_1 is likely to be reduced by the clustering of observations in clinics. An additional component of clustering arises because the four groups are aligned with nine practice groups that in turn are embedded in three hospitals. We acknowledge that there may be separate levels of clustering in the data due to hospital and below that due to practice groups.

However, the nine practice groups emanating from the 3 hospitals will be randomly distributed across the four groups of the stepped-wedge design in a manner that balances the four groups with respect to the characteristics of these groups. Because the practice groups and hospitals are cross-classified with the SWD groups, their effects on the statistical precision of the results will be much less than under a purely hierarchical arrangement.

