until thematic saturation is reached.⁵⁸ Interviews will be recorded with permission and transcribed verbatim, and analyzed iteratively (concurrent with ongoing qualitative work) using a general inductive approach.^{59–61} Analysis will be led by Drs. [name] and [name], in partnership with [name] (Co-investigator, Years 1-3), [name] (Years 3-5), [name] (Years 3-5) and [name] (Parent partner). Results summaries will be shared with interview participants, and with hospitals' DALTs, both to return results to participants and to member-check the credibility of findings.^{62,63}

6. Study Population and Setting

Eligibility Criteria. We will limit our analysis to children < 18 years of age admitted with the following common medical reasons for hospitalization: gastroenteritis/dehydration, skin and soft tissue infection, UTI, pneumonia, viral infection not otherwise specified, and influenza. These diagnoses comprise approximately 25% of all unscheduled PHM admissions nationally, and represent conditions that have been identified as appropriate for direct admission but not currently accepted for direct admission at the participating hospitals.^{25,39} Children with planned admissions (i.e. chemotherapy), those admitted to non-PHM Services (i.e. the ICU), and those transferred from other hospitals will be excluded.

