English, Spanish, Somali, Nepali or Arabic. (This response rate aligns with past work requesting parental participation in a survey during their hospital stay^{64,65}). To collect this parent-reported outcome, we will approach parents/guardians during their child's hospital stay, either by phone or in-person, keeping with each site's COVID-19 regulations. A research assistant will explain the study, and administer the survey via tablet or via personal cellphone to those parents/guardians who provide informed consent. Our sample size estimate for the relative number of direct admissions is dependent upon three assumptions/components of the direct admission process – first, that approximately 13% of children who are admitted to hospital will be seen by their PCPs prior to hospital admission (an

estimate derived from administrative data at NCH); second that these PCPs will contact the hospital for direct admission (a component of our direct admission intervention education); and third, that the PHM service will deem the child appropriate for direct admission and have a bed available. For this third criteria, we conservatively estimate that 80% of children referred for direct admission from PCPs will be accepted. Based on these assumptions, we estimate that 10% of children cared for by these PCPs will be directly admitted following rollout (Figure 2). Please note that our estimate that 13% of children who are admitted to hospital will be seen by their PCP is conservative; our PCP stakeholder partners have estimated that between 15 and 50% of their admitted patients are seen in their clinics prior to admission. For children considered for direct admission from urgent care centers, we anticipate that eligible urgent care providers will call to request direct admission in 80% of cases, and that 80% of these patients will be accepted. Our projected sample size of children admitted through the ED takes into account our assumption that these children may be more acutely unwell and/or clinically unstable. Correspondingly, we estimate that 70% of children who are admitted through the ED at children's hospitals with our target conditions will be eligible for inclusion, and that 95% of those who are admitted through the ED at our community hospital will be eligible for inclusion (given lower levels of acuity of children admitted to community hospitals).

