The second part of the calculation is to determine the power of a two-group comparison of a continuous outcome in the absence of clustering when the total sample-size is 711. Because there are 10 group-times in the post-period and 6 in the pre-period each with 106 observations, the split in the ESS between the post and the pre period is 444 and 267. The mean and standard deviation of the outcome in the pre-period is given by the above values for ED admissions; the mean is 85 and the standard deviation is 83. To determine the mean and standard deviation of the outcome expected in the post period, we take weighted averages of the DA and ED admission means and standard, using the total theorem of probability to compute marginal effects. The weight of DA to total patients is 19/106 = 0.094. The weighted average marginal mean and weighted average marginal standard deviation of the observations in the post period are 76.93 and 84.99, respectively. Because the sample-sizes are reasonably large, an asymptotic normal approximation is well justified (i.e., the true distribution of the outcome is bimodal will be averaged out). Given the ESS's and these means and standard deviations, a two-sided 0.05-level test has power of 0.23. In order to have 0.80 power, we would need a much larger effect-size. Specifically, the mean for the post-period would need to be approximately 66.5. Due to the small fraction of ED patients, this will only be plausible if there is a spillover effect of the intervention such that the outcome reduced for DA and ED patients, not just for DA patients.

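### A minimal pre-to-post change in the ED mean is too diluted a signal to support the plan's reading that DA children would otherwise have had ED children's outcomes

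*Combined protocol and SAP*

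**What the plan says.** Section D.5, Aim 1, restricts analysis (i) to post-crossover observations. A supplemental analysis then adds the pre-intervention ED children, in order to "test if there is a change in the mean ED outcome in the post-intervention period". Its purpose is modest: "to gain some insight into the closeness of the results from this analysis" with what patient-level randomisation would have given. The reading attached to it is less modest: "A result consistent with minimal change over time will support a finding that, in the absence of the intervention, the outcomes for DA patients"; the sentence then equates these with the outcomes of ED patients. No margin, power or definition of minimal is given.

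Selection into DA is described in D.7. The child must be seen by the PCP and referred, and the plan further assumes "that the PHM service will deem the child appropriate for direct admission and have a bed available". D.6 narrows the population: listed diagnoses only, planned admissions out, and "those admitted to non-PHM Services (i.e. the ICU), and those transferred from other hospitals will be excluded". The analysis (i) model adjusts for diagnosis, medical complexity, level of care, age, gender, race/ethnicity and payer, plus period, hospital and clinic. Figure 1 (D.2) lists disease severity among the patient factors, but the model has no direct measure of it.

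**The concern.** The logic of the check points the right way. If the children who move to DA differ from those who stay, the ED mean should shift when they leave. But they are a minority of admissions, so a large difference in their underlying outcomes becomes a small shift in the ED mean. That shift then has to be found in an outcome whose SD is about as large as its mean.

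With no margin set, a non-significant test would satisfy the sentence. The plan would then treat a null that was likely in any case as support for a causal reading of a non-randomised comparison. This matters because D.5 presents analysis (i) as the version that tests the Aim 1 hypothesis directly. The only question here is whether this one inference rule is justified.

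**Working it through.** **Inputs.** ED mean 85 min, SD 83; DA mean 40 min; planned difference 45 min (D.8). Post-period 190 DA and 870 ED (D.8). Pre-period ED 6 × 106 = 636, which also equals 1506 − 870 (D.8, Figure 2a). Two-sided 0.05, as used elsewhere in D.8; D.5 sets no level for this check. The documents give no residual SD, so the unadjusted 83 is an assumption.

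**The plan's own pre/post figure.** D.8 gives power only for analysis (ii): 85 (SD 83, effective n 267) against 76.93 (SD 84.99, effective n 444). SE = √(83²/267 + 84.99²/444) = 6.49; difference 8.07; power 0.237, against 0.23 stated. It reproduces closely.

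**Dilution.** Let w be the share of children who go by DA once it is available. Let d be the ED-route mean of the other children minus that of the DA-type children.
- Pre-period ED mean = w·μ_DA-type + (1 − w)·μ_other
- Post-period ED mean = μ_other
- Change = w·d, so the implied gap is d = change/w

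Here w = 190/1060 = 0.179. If selection accounted for the whole planned difference (d = 45), the change is 0.179 × 45 = 8.07 min, the size of shift for which D.8 states power of 0.23. If it accounted for half (d = 22.5), the change is 4.03 min.

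**Precision without clustering.**
- No period effects: SE = 83·√(1/870 + 1/636) = 4.33.
- With the period fixed effects of the analysis (i) model: the within-period information from the Figure 2a ED cells is Σ n_post·n_pre/n = 87·318/405 + 174·212/386 + 261·106/367 + 0 = 239.3. SE = 83/√239.3 = 5.37.

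| | No period effects | Period effects |
|---|---|---|
| 95% half-width for the ED change (min) | 8.5 | 10.5 |
| Same, divided by w (min of gap) | 47 | 59 |
| Power, d = 45 | 0.46 | 0.32 |
| Power, d = 22.5 | 0.15 | 0.12 |

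Clustering does not help. With a clinic random effect at ICC 0.05 and period effects, the SE is 6.12 and power for d = 45 is 0.26.

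**What a non-significant result is worth.** It occurs with probability 0.95 under no selection. Under full selection it occurs with probability 1 − 0.46 = 0.54 or 1 − 0.32 = 0.68. The ratios are 0.95/0.54 = 1.8 and 0.95/0.68 = 1.4. Against half selection they are 0.95/0.85 = 1.1 and 0.95/0.88 = 1.1.

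**Dependence on the SD.** An observed change of zero excludes a given gap when the half-width falls below w·d. The required R² is 1 − (SD/83)².
- d = 45: SD below 78.9 (R² about 0.10) without period effects, or 63.7 (about 0.41) with them.
- d = 22.5: SD below 39.4 (about 0.77) or 31.8 (about 0.85).

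**Modified design, direction only.** The shading of Figure 2b is not available. If the Figure 2a staircase applies, post-crossover cells hold 154 DA of 2,181 admissions (7.1%), and pre-crossover cells already hold 30 DA of 608 (4.9%). The DA-type share of the pre-period ED group is then (w_post − w_pre)/(1 − w_pre), which is smaller than w_post. Both features weaken the check further.

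**The case against.** The strongest reply is that little hangs on this sentence. The check is labelled supplemental, its aim is only some insight, and the verb is support, not establish. D.5 already calls the analysis (i) coefficient an association, and analysis (ii) keeps the randomised contrast. All of that stands, and it limits the consequence. It does not supply the missing margin.

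A reader might infer that a null carries no information. That is too strong. A change of exactly zero favours no selection over a 45-min gap by a normal likelihood ratio of exp(½·(8.07/4.33)²) = 5.7, or exp(½·(8.07/5.37)²) = 3.1 with period effects, which is modest support. Against half the gap the ratio is only 1.5 or 1.3, and a merely non-significant change is weaker still.

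The results depend on the unadjusted SD. Without period effects, a modest R² of about 0.10 would let a zero change exclude full selection. Excluding half selection would need far more than can be assumed.

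A reader might also rerun the check at the lower shares that appear in the text. The documents do not support them as trial-wide shares. The line "The weight of DA to total patients is 19/106 = 0.094" is an arithmetic slip: 19/106 is 0.179, and the stated post-period mean of 76.93 uses 0.179. The statement that "we estimate that 10% of children cared for by these PCPs will be directly admitted following rollout" follows from the PCP assumptions (13% × 80%), while urgent care has separate ones. Figure 2b cannot safely be turned into a bound on the gap either, because the simple formula assumes no DA before crossover.

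Finally, eligibility removes some severity differences: D.7 expects 70% of ED admissions at the children's hospitals and 95% at the community hospital to qualify. Any remaining selection may therefore be small and could run in either direction. The documents do not show that selection is present, only that this check could not rule it out.

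**Conclusion.** Wrong as written, limited to this one supplemental inference rule. On the planned counts, an ED change caused by selection as large as the whole 45-min effect would be missed in 54% of trials (68% with period effects). Selection half that size would be missed in 85% (88%). Nor would a precise null settle the matter, because D.8 itself says of the larger effect needed for 0.80 power in analysis (ii) that "this will only be plausible if there is a spillover effect of the intervention such that the outcome reduced for DA and ED patients". Faster ED care after rollout could cancel a shift from selection or produce one without it.

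The size rests on SD 83 in both periods, no clustering, a stable DA-type case mix, no DA before crossover and no spillover. A reader might conclude that the primary estimate is biased or the trial's randomised evidence compromised. The documents do not support that: the analysis (i) estimate does not depend on this check, and analysis (ii) is untouched.

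**What to change.** Replace the inference sentence in D.5 with wording such as:

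> We will report the adjusted pre-to-post change in the ED mean with its 95% CI. We will also report that change and CI divided by the change in DA share between pre- and post-crossover admissions, (w_post − w_pre)/(1 − w_pre), which equals the post-period DA share when there is no pre-crossover DA. This gives the range of selection gaps compatible with the data if the intervention had no effect on ED patients and the DA-type case mix was stable. It will be shown beside the estimated DA-ED difference. A non-significant change will not be read as showing that DA and ED patients are exchangeable.

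Keep conclusions from analysis (i) worded as an adjusted association, in line with how D.5 describes its coefficient, and name analysis (ii) as the randomised comparison.

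The cost is one SAP wording change and one rescaled interval from a model already planned, with no new data. The downside is a softer causal claim for analysis (i).

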We will first determine crude differences in baseline clinical and sociodemographic characteristics, and in our primary and secondary outcomes, between children admitted directly and through EDs, using t-tests and chi-square tests as appropriate. However, because these unadjusted analyses do not adjust for observed predictors related to direct and ED admission, including temporal trends, for our main analyses we will use regression models. Because all patients receive some form of clinical care at the hospital irrespective of form of admission, there is no censoring associated with the measurement of time to clinical care. Therefore, standard regression models may be used. Patient characteristics incorporated in models will include diagnosis, medical complexity,⁴⁹ level of care (observation versus inpatient), as well as age, gender, race/ethnicity and payer. The statistical model for our direct patient-level comparison of direct admission (DA) versus ED admission patients (analysis i) is

$$Y_{ijht} = \beta_0 + \beta_1 D A_{ijht} + \beta_2 x_{ijht} + \beta_{3t} + \beta_{4h} + \theta_{jh} + \varepsilon_{ijht}$$

in which Y_{ijht} is the outcome variable for patient *i* seen by clinic *j* at hospital *h* at time *t*; DA_{ijht} is a binary variable indicating whether the patient was admitted via direct admission ($DA_{ijht} = 1$) or the ER ($DA_{ijht} = 0$), x_{ijht} is a vector of patient-level controls and θ_{jh} is a random effect for clinic within hospital. In addition, the model includes fixed-effects for time-period, β_{3t} , and hospital, β_{4h} , to capture the general unstructured trend across calendar time and hospitalspecific effects, respectively. The key coefficient of interest is β_1 , which captures the association of a patient being admitted directly versus by an ED with the outcome. A crucial feature of this analysis is that the predictor of primary interest, DA, varies within clinic and time-period mitigating almost all forms of clustering. Therefore, although the data are clustered by clinic and time, the primary source of information about the association of DA with the outcome is from contrasts within clinic and time-period. Hence, accounting for time-period and clinic effects is likely to strengthen the statistical significance of our results.

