To test our hypothesis that children with UTI, skin and soft tissue infections, and co-morbid complex chronic illness will experience the greatest benefits from direct admission relative to children admitted with other clinical diagnoses, we will evaluate group-level heterogeneity of treatment effects (HTE) by conducting subgroup analyses as specified *a priori*. Although there is no prior literature about the relative benefits of direct admission for these subgroups, this hypothesis is derived from our deliberative discussions with multidisciplinary stakeholders, based on their lived experiences. Our anticipated sample size for subgroups is derived from national statistics about pediatric inpatient stays (HUCPnet.ahrq.gov), shown in Table 3. Although our assessment of HTE will follow methodological guidance that all subgroups be specified a priori, we will consider other subgroup analyses based on recommendations from Parent Partners and

hospitals' DALTs.^{55,56} Subgroup analyses will be performed by estimating an analogous model to that for analysis (i) given above for the subgroups of interest. To evaluate whether the effect of the direction admission intervention varies significantly across subgroups, we will augment the model specified in Aim 1 analysis (i) with a predictor for the product of the subgroup-defining variable and DA; the coefficient of the additional variable is referred to as an interaction effect and its value captures the extent to which the effect of DA differs between one level of the subgroup to the other. This approach is based on the recommendations by Kent et al., who recommend analysis and reporting of multivariate riskbased HTE to account for the fact that patients have multiple characteristics simultaneously that affect the likelihood of benefiting from an intervention.^{56,57}

Aim 3. Applying mixed qualitative and quantitative methods, identify barriers to and facilitators of implementing direct admission processes.

To determine the impact of our direct admission intervention and to inform post-project implementation in other health systems, we will conduct a mixed-methods process evaluation applying the RE-AIM implementation framework to

Table 4. Components of mixed methods process evaluation using RE-AIM Framework				
Domain and Definition	Approach			
REACH: the % and	Monthly reports to primary care practices reporting the			
characteristics of children	number and % of eligible children admitted via direct			

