8. Sample Size and Power. Our projected sample size is shown in Table 5 and Figure 2. Based on the conservative assumptions above, we anticipate that 190 children and adolescents will be directly admitted and 1506 will be admitted through the ED. Of those admitted through the ED, 870 will be during post time-periods. Therefore, for analysis (i) there will be 190 direct admissions and 870 concurrent control ED admissions. Because the effect of all forms of clustering in analysis (i) of Aim 1 are minimal, we illustrate the statistical power for this analysis by using a two-group t-test. To inform our effect size determination, the PHM program at Lowell General Hospital (Lowell, MA), which has a well-established direct admission program, collected timeliness data from April-July 2018, applying the same eligibility criteria and definition proposed for this study. ED timeliness data was similarly derived from Lowell and PMRC-E. We found that mean time to clinical care for ED admissions was 85 min [SD 83 min], and mean time for direct admissions was 40 minutes [SD 28 min].

With the above means and standard deviations, a two-sided 0.05-level test that allows for unequal standard deviations performed in the context of analysis (i) of Aim 1 has power well in excess of 0.99. There is also substantial power for subgroup analyses. For example, the power of a subgroup analysis that involves 10% of the sample (applied evenly across clinics and time-intervals) has power of 0.98. It is only when the subgroup is as small as 5% that power falls below 0.80. These power calculations can be performed using self-calculation or a variety of software packages. In this instance, it was performed using Satterwaite's approximation (i.e., evaluating a pooled variance to approximate the sampling distribution of the actual test-statistic by a t-distribution) under nQuery.

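### Power for analysis (i) and its subgroups assumes unequal SDs (28 vs 83 min), but the model as written makes no unequal-variance provision; a conventional fit would not deliver the stated subgroup power.

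*Combined protocol and SAP*

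**What the plan says.** Section D.8 (Sample Size and Power) takes a mean of 85 min (SD 83) for ED admissions and 40 min (SD 28) for DA, with 190 DA and 870 concurrent ED patients. It describes the calculation as "a two-sided 0.05-level test that allows for unequal standard deviations performed in the context of analysis (i) of Aim 1", made by Satterthwaite's approximation, that is, "evaluating a pooled variance to approximate the sampling distribution of the actual test-statistic by a t-distribution". It reports full-sample power well above 0.99. For subgroups it says that "the power of a subgroup analysis that involves 10% of the sample (applied evenly across clinics and time-intervals) has power of 0.98" and that "It is only when the subgroup is as small as 5% that power falls below 0.80".

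Section D.5 (Statistical Analysis Plan, Aim 1) argues that ordinary regression is adequate because nothing is censored. It writes model (i) with fixed effects for period and hospital, patient covariates, a term that "is a random effect for clinic within hospital", and one residual term. No distribution is given for the residual.

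Aim 2 uses that model twice: within subgroups, by "estimating an analogous model to that for analysis (i) given above for the subgroups of interest", and for effect modification, where "we will augment the model specified in Aim 1 analysis (i) with a predictor for the product of the subgroup-defining variable and DA". Neither part of Section D.5 names a robust variance estimator, separate DA and ED residual variances, or a transformation.

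**The concern.** The power section relies on a test suited to the plan's own inputs, in which the variances differ almost ninefold (83² = 6889 against 28² = 784). The analysis section does not carry that feature over. A conventional mixed-model fit of the equation as written estimates one residual variance, dominated by the large, more variable ED group, and applies it to the small, less variable DA group as well. The standard error of the DA coefficient is then too large.

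Two things are at stake: the width of the confidence interval on the primary contrast, and whether Section D.8's subgroup statements describe the analysis that will be run. UTI, which Hypothesis 2 names and Table 3 projects at 11% of the sample, sits close to where a common-variance fit reaches 0.80.

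**Working it through.** **Inputs.** From Section D.8: means 40 and 85 min (difference 45), SDs 28 and 83, n = 190 DA and 870 ED, two-sided 0.05. From Table 3: UTI 11%, skin and soft tissue infection 16%, complex chronic disease 36%. A subgroup of share f has 190f DA and 870f ED patients. The closed forms ignore clustering, as Section D.8 does for analysis (i).

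**1. Reproduce the plan (unequal variances).** SE = √(784/n₁ + 6889/n₂), Satterthwaite df, noncentral t.
- Full sample: SE = √(4.126 + 7.918) = 3.47 min; power above 0.99.
- 10% (19 vs 87): SE = √(41.26 + 79.18) = 10.97; df 86.6; power 0.982. The stated 0.98 reproduces.
- 5% (9.5 vs 43.5): SE = 15.52; power 0.81 (0.797 at 9 vs 43). Power crosses 0.80 at 4.9%, so the plan's 5% statement holds to rounding.

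**2. One residual variance.** The model's SE is s_p·√(1/n₁ + 1/n₂), with s_p the pooled SD. The estimate still varies with the true SE from step 1. Power ≈ Φ[(45 − t·SE_model)/SE_true].
- Full sample: s_p = 76.1; SE_model = 76.1 × √(1/190 + 1/870) = 6.10, against a true 3.47. Ratio 1.76. The 95% half-width is 12.0 instead of 6.8 min. Power stays above 0.99.
- 10%: s_p = 76.4; SE_model = 19.34; t = 1.983, so rejection needs 38.35 min. Φ[(45 − 38.35)/10.97] = Φ(0.606) = 0.73.
- 5%: SE_model = 27.44; t = 2.008, so rejection needs 55.09 min. Φ(−0.65) = 0.26.

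| Share of sample | Unequal variances | One variance |
|---|---|---|
| 5% | 0.81 | 0.26 |
| 10% | 0.98 | 0.73 |
| 11% (UTI) | 0.99 | 0.79 |
| 16% (skin infection) | >0.99 | 0.96 |
| 36% (complex chronic) | >0.99 | >0.99 |
| Power reaches 0.80 at | 4.9% | 11.2% |

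Type I error under one variance at 10% is about 0.0005 in the closed form and 0.003 in a simulation with skewed (gamma) data, so the test is conservative.

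**3. Sensitivity.**
- Two-group simulation with gamma data, one variance: 0.78 to 0.79 at 10%, 0.85 for UTI, 0.98 for skin infection.
- Mixed-model simulation of model (i), without patient covariates (70 clinics, hospital and period effects, gamma outcome, clinic ICC assumed 0.05 as in Section D.8, 1,500 runs): 0.74 at 10% and 0.82 for UTI. In the full sample the default SE averaged 6.00 against an actual SD of 3.28, and the 95% interval covered about 99.9%.
- Ordinary least squares with period and hospital indicators, no clinic effect: 0.68 at 10%, slightly below the two-group range.
- Figure 2b, summing cells from each group's crossover onward, gives 154 DA and 2,027 ED. The SEs are then 6.72 and 2.91, and the one-variance cut-off is 12.2%.

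**4. Does allowing unequal variances restore the claims?** In regressions with period and hospital effects but no clinic effect, arm-specific variances gave 0.97 at 10% and about 0.75 at 5%. In the mixed-model simulation, cluster-robust CR2 standard errors gave 0.96 at 10% and 0.62 at 5%.

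**The case against.** The best defence is that the plan never states a constant variance. One residual symbol with no distribution is compatible with unequal variances, and Section D.8 ties its unequal-SD test to analysis (i). That shows intent, and it makes the loss conditional on how the model is fitted. But the wording sits in a power section that presents the t-test as an illustration, and nothing in Section D.5 turns it into a regression specification.

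Covariates are a second defence, since model (i) adjusts for diagnosis, complexity, level of care and demographics. The plan gives no R². If covariates explained 5%, 10% or 20% of the variance (both SDs multiplied by √(1 − R²)), one-variance power at 10% would be 0.76, 0.80 or 0.86. That narrows the gap without closing it; regaining 0.98 would need about 45%.

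It is also fair that the consequence is limited. The only Table 3 subgroup below 10% is influenza (3%), which Hypothesis 2 does not name and which is already below the plan's own 5% boundary.

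A reader might infer that the primary comparison is underpowered, that false positives are inflated, or that the 0.98 is miscalculated. None of these holds: full-sample power exceeds 0.99 either way, the error is conservative, and the 0.98 is right for the test it names. Nor is the absence of interaction power an error. The 0.98 is correct for the within-subgroup models and makes no claim about the interaction.

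**Conclusion.** The point stands as a mismatch between Sections D.5 and D.8, conditional on a conventional one-variance fit. On that condition, the primary interval is about 1.8 times too wide. Power for 45 min in a 10% subgroup is about 0.73 to 0.79 before covariate gain, and Section D.8's 5% boundary becomes about 11%. Among the Hypothesis 2 subgroups only UTI is materially affected (about 0.79 to 0.85); skin infection stays at about 0.96 to 0.98 and complex chronic illness above 0.99. These figures assume the plan's means and SDs, 190/870, and the same DA share and SDs in every subgroup.

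It would go too far to say that Aim 2 as a whole loses its power or that the plan commits to a common variance. The change should be made because it is cheap and settles the variance method for the primary contrast before the data are analysed.

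**What to change.** **Section D.5, after model (i), add:** *For analysis (i) and both Aim 2 models, the residual variance will be allowed to differ between DA and ED patients (separate residual variances, with Satterthwaite degrees of freedom). Cluster-robust standard errors by clinic with a small-sample correction will be reported as a check.*

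Cluster-robust CR2 standard errors as the main method would be acceptable, with less power in subgroups near 5% of the sample.

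**Section D.8, add:** *The 0.98 and 5% figures assume this unequal-variance analysis. They refer to the full 45-min effect within one subgroup, not to the DA-by-subgroup interaction.* Detectable interaction sizes should not be inserted, because they would rest on effect sizes and equal-SD assumptions that the plan does not supply.

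**Cost.** A few sentences, with no new data and no design change. The model gains one variance parameter, and estimates will be less stable in very small subgroups.
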